5.8.1. Reasons for Study Drug Interruption/Discontinuation

Any reason for study drug interruption/discontinuation will be recorded in the eCRF. Such reasons include, but are not limited to the following:

- Reasons Related to AE:
 - Initiating or continuing study drug would place the subject at undue hazard as determined by the Investigator: in particular treatment failure or events, e.g., thrombosis, related to non-compliance with the anticoagulant regimen
 - When subjects reach a primary endpoint or a key safety endpoint, the treating physician needs to decide if OAC medication will be permanently discontinued, interrupted, modified or continued. In case of intracranial bleeding the protocol mandates stopping the study treatment.
 - SAE or other safety concern that is related to study drug treatment;
 - Concurrent increase in aspartate transaminase (AST)/alanine transaminase (ALT) > 3 X upper limit of normal (ULN) and bilirubin > 2 X ULN in the absence of a known cause (e.g., viral hepatitis, cholelithiasis) and where a causal relationship cannot be ruled out;
 - Major life-threatening bleeding (as defined in the CEC Charter, also see Section 17);
 - CrCL decreased to <15 mL/min, confirmed by repeat testing at least one week later, or need for renal dialysis.
- Death;
- Withdrawal of Informed Consent;
- Lost to Follow-up (every attempt will be made by the Investigator to avoid having subjects “lost to follow-up”);
- Pregnancy;
- Termination of all or part of the study by the Study Oversight Committee acting in concert with the DSMB and the Sponsor.
- Post randomization changes (other than CrCL decreased to <15 mL/min or need for renal dialysis) in health status related to study exclusion criteria should not automatically lead to study drug interruption or discontinuation unless continuing study drug places the subject at undue hazard as determined by the Investigator. Such situations should be handled on a case-by-case basis. The Investigator should consult with the CRO medical monitor if a subject has a post randomization change in health status that puts the subject into an exclusion criterion.

Those subjects who discontinue study participation after the initiation of study medication will have study procedures terminated at the time of discontinuation from study with the EOT Visit (Section 6.5). If the subject discontinued study treatment due to an AE, the Investigator will follow the subject until the AE has resolved or stabilized.

5.8.2. Subjects with Study Drug Interruptions/Discontinuations

The Investigator should call the CRO medical monitor in case of any questions regarding how to handle a study medication interruption and/or discontinuation.

Suspension/Interruption: The date/time of the last dose, the reason for the interruption, and other required details will be recorded in the eCRF. Reasons for interruption include but are not limited to: development of clinical contraindications for any study drug (according to the label of the respective drug). During each interruption of anticoagulant or antiplatelet therapy, subjects are evaluated to determine whether the subject can safely resume the study drug.

Discontinuation: The date/time of the last dose, the reason for the discontinuation, and other required details will be recorded in the eCRF. For some potential reasons for discontinuation of study drug see Section 5.8.1 and locally approved drug label.

During a study drug interruption or after study drug discontinuation, a subject can be placed on another antithrombotic therapy per local guidelines and Investigator discretion. All randomized subjects, including those who discontinued study medication, will be followed through the overall end of the study for the primary and secondary efficacy and safety endpoints and SAEs. If the subject has an onsite visit, it is expected that vital signs will be obtained along with any laboratory assessments deemed appropriate by the Investigator.

If a subject who discontinues study drug also withdraws consent, in writing, for participation in the study, the protocol-specified consent withdrawal procedures (Section 5.8.3) must be completed.

If the subject interrupts (or discontinues) study drug due to an AE, the Investigator will follow the event until it has resolved or stabilized.

5.8.3. Withdrawal of Consent from Study Participation

In accordance with the Declaration of Helsinki and other applicable regulations, a subject has the right to withdraw consent for participation in the study at any time and for any reason without prejudice to his/her future medical care by the physician or at the institution.

If a subject withdraws consent to participate in the study, the Investigator will complete and report the observations as thoroughly as possible up to the date of consent withdrawal and including the date of the final dose of study medication. The Investigator will clearly document the reason for consent withdrawal in the medical record and will complete the associated eCRF. Under no circumstances will a subject have to undergo any study visit if he/she has expressed the will to leave the study; however, every attempt should be made to have the subject complete the 30-day Follow-up Visit (Section 6.6), be followed until the end of the study for study endpoints and SAEs (Section 6.7), and provide the subject with the information needed for transition to standard of care VKA (Section 6.5.1). If this is not possible, the subject will be offered the opportunity to consent to one of the following:

- Providing information about his/her own health status by telephone or other means until the 30 days post last dose,
- Allowing the query of their medical records,
- Allowing the use of public databases to determine subject status until the end of the study.

5.8.4. Subject Replacement

As an endpoint study with enrollment continuing until the required number of adjudicated events are reached, there is no need to formally replace a subject.

5.8.5. Subject Re-screening Procedures

There will be no re-screening of subjects for this study.

6. STUDY PROCEDURES

6.1. Screening Visit

From 12 hours to 5* days, i.e., until 23:59 of the 5th* day after the successful TAVI and prior to randomization, all screening procedures will be completed. See [Table 17.1](#) for a listing of all screening procedures.

The following activities will be performed 12 hours and 5* days, i.e., until 23:59 of the 5th* day after the successful TAVI (See inclusion criteria #1 for definition of successful TAVI), **prior to randomization and after obtainment of written informed consent (no screening procedures may be performed unless written informed consent has been obtained):**

*If subject is waiting on a decision on pacemaker surgery, then can extend to 7 (7th) days

The informed consent form (ICF) must be signed by the subject before any study-specific procedure including randomization. A Screening eCRF must be completed for every subject with a signed ICF. Any protocol-specified study qualification procedures/tests not already done as part of routine care will need to be conducted after the ICF has been signed and before randomization.

- Enter subject into IXRS
- Check the most recent results from local laboratory tests done within the 15 days prior to randomization against the inclusion/exclusion criteria. Creatinine and complete blood count (CBC) must be available from blood draws after TAVI with the subject being clinically stable. CrCL should be calculated by the Cockcroft-Gault formula as described in [Section 17.7](#). For subjects already on a VKA, review and record most recent INR results
- Record demographic information (date of birth/age, sex, ethnicity, and race)
- Record medical / surgical history (including bleeding history)
- Eligibility evaluation (inclusion and exclusion criteria). No subject may be randomized unless all eligibility criteria are met.
- Serum pregnancy test for female subjects who are of childbearing potential.

6.2. Randomization Visit (Day 1)

Randomization must take place within the evening of the day of TAVI and 5* days, i.e., until 23:59 of the 5th* day provided that the TAVI procedure has been judged as successful (See inclusion criteria #1 for definition of successful TAVI), and the subject is qualified based on all the protocol defined inclusion/exclusion criteria. Randomization should occur as soon as possible after signing the informed consent, given eligibility is confirmed.

*If subject is waiting on a decision on pacemaker surgery, then can extend to 7 (7th) days

- Check subject against inclusion/exclusion criteria including the most recent lab results.
- Record type of TAVI device inserted into subject in the eCRF

- Enter elements for EuroSCORE 1, EuroSCORE 2, Society of Thoracic Surgeons (STS), CHAD, and HAS-Bleed scores into the eCRF
- Contact IXRS for randomization and pre-declaration of OAP.
- Prior to any study drug administration or other tests, the subject must complete the PACT-Q1 and EuroQoL (EQ-5D-5L) questionnaires. These will be collected and uploaded into the data base by the CRO via the eCRF.
- If ECG was performed as part of routine medical practice, record the results. If not obtained as part of routine medical practice, collect a pre-dose ECG for baseline measurement and record results.
- Update medical / surgical history (including bleeding history) since screening
- Physical Examination including
 - Record vital signs (blood pressure and heart rate after the subject has been resting at least 5 minutes in a sitting position; body temperature, and weight)
 - Record height
- Record prior (since screening) medications and review as per exclusion criteria.
- If echocardiogram (transthoracic echo [TTE] or transesophageal echo [TEE]) was performed pre-TAVI per local standard of care, the information will be recorded as specified in the eCRF.
- Draw blood for analysis by an accredited/certified local laboratory (Section 9.9) (if recent [within the 15 days before randomization] are available from standard of care, these values may be used instead of requiring an additional blood draw). Creatinine and CBC must be available from blood draws after TAVI and the subject must be clinically stable. CrCL should be calculated by the Cockcroft-Gault formula as described in Section 17.7 and the results need to be available prior to the 1st dose of study drugs for subjects randomized to Edoxaban. Include a liver panel only if recent (within the 15 days before randomization) results are not already available.
- For childbearing potential female subjects, a urine pregnancy test (e.g., dipstick test) will be performed at Randomization, 3 months, 12 months, 24 months, and End of Treatment Visits. Furthermore, pregnancy tests will be carried out whenever there are clinical indications for the existence of a pregnancy.
- First administration of assigned study medication **within 24 hours of randomization**; however, **NO EARLIER** than the morning after successful TAVI.
- Record date/time of first study medication administration in eCRF
- Instruct subject on the use of study medication (see Section 3.1)
- Instruct subject on the use of the memory aid
- Dispense assigned OAC

- Daiichi Sankyo supplies study subjects with Edoxaban. VKA and OAP may be supplied by the site or via prescriptions issued either by the site or attending physician. See Section 3.1 about OAP administration.
- Assessment and recording of (S)AEs and suspected clinical events will start immediately after signed informed consent and continue until 30 days after the end of treatment with study medication.

The randomized treatment strategy is implemented after randomization without any undue delay.

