5.1.2. Method of Treatment Allocation

Prior to randomization of a subject, all eligibility criteria must be met and a signed informed consent obtained.

Enrollment and randomization must occur between the evening of the day of TAVI and 5* days, i.e., until 23:59 of the 5th* day provided that the TAVI procedure has been judged as successful (See inclusion criteria #1 for definition of successful TAVI) and the subject is qualified based on all the protocol defined inclusion/exclusion criteria. All sites will be required to maintain a record of all subjects screened for the trial. The reason for screen failure must be documented in the subject's records. Subjects must be randomized without delay and administered their first dose of study medication within 24 hours post randomization; however, NO EARLIER than the morning after successful TAVI. Randomization will be performed using the IXRS system for subjects meeting all eligibility criteria. The directions on how to use the system will be provided in the IXRS Quick Reference Manual. The randomization scheme will be securely stored at the statistical department of the database management center.

*If subject is waiting on a decision on pacemaker surgery, then can extend to 7 (7th) days

Based on this information, the system will assign a unique subject identification number and treatment for that subject. Trial randomization will not be blinded and once subject is assigned to a treatment arm, no treatment cross-over is permitted. Subjects will be randomly assigned in a 1:1 ratio to receive Edoxaban or VKA. The Investigator will pre-declare the type (if any) P2Y₁₂ antagonist or ASA treatment and its projected last dose prior to the randomization (pre-declaration, via the IXRS).

The Investigator's knowledge of the treatment must not influence the decision to enroll a particular subject or affect the order in which subjects are enrolled.

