5.1.3. Blinding

This study is open-label.

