10.2. Perception Anticoagulant Treatment Questionnaire (PACT-Q)

The Perception of Anticoagulant Treatment Questionnaire (PACT-Q) was developed to assess subjects' expectations of, and satisfaction with their anticoagulant treatment. The psychometric properties of the PACT-Q have been reported previously. The PACT-Q consists of two modules. The first module, PACT-Q1, contains 7 items, each individually scored from 1 to 5, with higher score indicating higher subjects' expectation for their treatment. The second module, PACT-Q2, is constituted of two dimensions: Convenience (11 items) and Anticoagulation Treatment Satisfaction (7 items). Items in the Convenience dimension are reversed scored, summed and rescaled on a 0 to 100 scale such that the higher the score indicates a treatment to be more convenient and less burdensome as perceived by the subject. Items in the Anticoagulation Treatment Satisfaction dimension are summed and rescaled on a 0 to 100 scale. Higher score indicates higher satisfaction with anticoagulation treatment.

The PACT-Q1 will be administered to study subjects at randomization. The PACT-Q2 will be administered to study subjects at 3 months and either 12 months or the EOT whichever comes first. A copy of the PACT-Q1 and PACT-Q2 will be provided to the sites.

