11.4.4. Health Economics Outcome Research (HEOR) Analyses

For healthcare resource utilization, proportion of subjects with hospitalization, number of hospitalizations, and length of hospital stay related to cardiovascular events of protocol

interest during the study will be described using summary statistics and compared between treatments.

For the PACT-Q, the absolute PACT-Q1 item scores and change from baseline values at the 12 months (or end of treatment if earlier) will be described using summary statistics and compared between treatments. In addition, the PACT-Q2 Convenience and Treatment Satisfaction scores will be summarized at each scheduled time point (Table 17.1) and compared between treatment groups.

For the EQ-5D-5L, the absolute and change from baseline values for the five domain scores, the EQ-5D-5L index value, and the EQ VAS score will be described using summary statistics by scheduled time point and compared between treatments.

Additional details will be provided in the SAP.

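### No section requires the baseline EQ-5D-5L and PACT-Q1 before the open allocation is known, so the planned EQ-5D-5L change scores may rest on a post-allocation baseline

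*Combined protocol and SAP*

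**What the plan says.** Section 6.2 (Randomization Visit) sets the timing rule for the baseline questionnaires: "Prior to any study drug administration or other tests, the subject must complete the PACT-Q1 and EuroQoL (EQ-5D-5L) questionnaires". The bullet just above it in the same list reads "Contact IXRS for randomization and pre-declaration of OAP".

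Section 10.2 says "The PACT-Q1 will be administered to study subjects at randomization". Section 10.3 and Table 17.1 footnote i likewise give randomization as the EQ-5D-5L time point and do not say whether it comes before or after the IXRS call. Section 6.1 lists what must be done before randomization, and neither questionnaire is on that list.

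On blinding, Section 5.1.3 says "This study is open-label" and Section 5.1.2 says "Trial randomization will not be blinded and once subject is assigned to a treatment arm, no treatment cross-over is permitted". Section 5.1.2 also has subjects "administered their first dose of study medication within 24 hours post randomization".

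Section 11.4.4 plans, for the EQ-5D-5L, "the absolute and change from baseline values for the five domain scores", together with the index value and the VAS, by scheduled time point and compared between treatments. For the PACT-Q1 it names item scores and a change from baseline at 12 months, or at end of treatment if earlier.

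**The concern.** A baseline earns its role because randomization makes it independent of treatment. Once the subject knows the arm, the answer can depend on the arm, and the measurement becomes an early outcome. Subtracting it from a later value then mixes the treatment effect with the reaction to allocation.

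The two instruments are exposed in different ways. The EQ-5D-5L includes an anxiety/depression domain and a self-rated VAS, and its baseline feeds change scores compared between arms. The PACT-Q1 asks what the subject expects of treatment, which may well differ between someone just told they will take edoxaban and someone just told they will take an INR-monitored VKA. At stake is how the patient-reported comparisons are read. These are listed among the other endpoints in Section 7.4.3, and the synopsis plans no formal testing for such endpoints.

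**Working it through.** The plan gives no figure to reproduce. The check is a comparison of the sections, followed by short algebra.

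**Step 1: is completion before allocation required anywhere?**

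| Place | Limit on the baseline questionnaires |
|---|---|
| 6.1, activities before randomization | Questionnaires not listed |
| 6.2 | Before study drug or other tests |
| 10.2, 10.3 | At randomization, no order |
| Table 17.1, footnote i | At randomization, no order |

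The IXRS call is neither study drug nor a test, so none of these rules places the questionnaires before it. The protocol does state such an order elsewhere: Section 5.1.2 asks for the antiplatelet pre-declaration ahead of randomization.

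**Step 2: is there room for a compliant site to do it afterwards?** Yes. Section 6.2 allows randomization from the evening of the TAVI day but no first dose before the next morning, and otherwise allows up to 24 hours between the two. The other-tests limit narrows this room without closing it. Section 6.2 accepts an ECG from routine practice and laboratory values from standard of care within 15 days before randomization (creatinine and CBC from after TAVI). Where those already exist, no ECG or blood draw need force the questionnaires to come early. Where the eligibility blood is drawn at this visit, the rule does in effect put the questionnaires before randomization.

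**Step 3: effect on the EQ-5D-5L change score.** Let m be the mean baseline that either arm would give before allocation, equal in expectation by randomization. Let s_E and s_V be the mean shifts caused by knowing the arm (edoxaban, VKA), averaged over all subjects in the arm, so that anyone who answered before allocation contributes zero. Let d = s_E - s_V, and let F_E and F_V be the follow-up means.

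- Difference in change = [F_E - (m + s_E)] - [F_V - (m + s_V)] = (F_E - F_V) - d.
- Difference in absolute follow-up values = F_E - F_V, with no d.
- If the SAP used baseline as a covariate with slope b, the bias would be about -b × d. Section 11.4.4 specifies no such model.

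The bias in the change score is therefore -d. It is zero if both arms shift equally or if every subject answers before allocation. The documents give no value for s_E, s_V or the share of subjects affected.

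**Step 4: PACT-Q1.** Section 10.2 and footnote i give the PACT-Q1 once, at randomization, and the PACT-Q2 at 3 months and at 12 months or EOT. The PACT-Q2 is a different module (convenience and satisfaction). With one PACT-Q1 value per subject there is no later value to subtract from, so the change score named in Section 11.4.4 does not exist under this schedule. Only the absolute between-arm comparison remains. If every subject answers before allocation, its expected difference is zero and it checks baseline balance. If some answer afterwards, it mixes that check with the reaction to the assigned arm.

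**The case against.** The strongest reply is that the text permits late completion but does not direct it. That is right. A reader might infer from the bullet order in Section 6.2 that the questionnaires follow randomization. The documents do not support this: the bullets are unnumbered, and items listed later, such as the medication review against the exclusion criteria, belong before randomization because Section 5.1.2 requires all eligibility criteria to be met first.

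A reader might also infer that the questionnaires may be completed at any time in the 24 hours before the first dose. That window governs the dose. The questionnaires must also precede other tests, and three places put them at randomization. The point stands only because none of these limits is the IXRS call.

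A third reply is that little is at stake. Absolute EQ-5D-5L values at follow-up do not use the baseline, most EQ-5D-5L domains have no obvious reason to react to allocation within a day, and the endpoints are exploratory. All of this stands, and it limits the point to a small one.

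Finally, for the PACT-Q1, asking about expectations of the assigned treatment after allocation could be a deliberate choice. The documents do not say which is meant.

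**Conclusion.** The protocol allows the baseline EQ-5D-5L and PACT-Q1 to be completed with the arm known. For the EQ-5D-5L this puts the planned between-arm change from baseline at risk of a bias of -d, where d is the differential shift. The size is unknown: the documents give no basis for any value of d, and any figure supplied for it would be a guess. The result assumes that at least some subjects answer after learning their arm and that the two arms react differently; the text shows that the first is permitted, not that it occurred.

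A reader might infer that the PACT-Q1 change score is biased as well. It is not, because it cannot be computed; the PACT-Q1 concern is confined to expectation scores that may reflect the assignment. Nor does the point reach the absolute follow-up comparisons of the EQ-5D-5L, the four primary hypotheses, their error control or the target of 320 events. It is a minor but nearly free improvement.

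**What to change.** In Sections 6.2 and 10.3 and in Table 17.1 footnote i, require the EQ-5D-5L after consent and before the IXRS randomization call, and record the completion time.

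For the PACT-Q1, state its purpose. If it is a baseline measure, apply the same order there and in Section 10.2, and describe its between-arm comparison in Section 11.4.4 as a check of baseline balance only. In either case, remove the PACT-Q1 change score from Section 11.4.4 or reconcile it with the schedule.

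For subjects already enrolled, flag baselines known to have been completed after randomization and repeat the EQ-5D-5L change analysis without them. Because that exclusion depends on something that happened after randomization, present it as a sensitivity analysis and read it beside the absolute follow-up comparison, which needs no baseline.

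The cost is a change in the order of steps at one visit, with no added visit or instrument; Section 10.3 puts the EQ-5D-5L at 1 to 2 minutes. The wording change would go through the amendment approvals in Section 15.7 and could travel with the next amendment.
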